Subjects to be studied will have histologically confirmed NASH as defined by the NIH NASH CRN (Kleiner 2005) and determined by a qualified central pathologist's reading (see [Appendix 1](#)). Historical biopsy results within 6 months of the first Screening visit may be used for inclusion into the study; otherwise, a liver biopsy must be obtained for assessment. Subjects must have a NAS of at least 4, with a minimum of 1 point in each of the three components, along with the presence of either Stage 2 or 3 fibrosis. Subjects with no (Stage 0) or minimal (Stage 1) fibrosis and cirrhosis (Stage 4) will be excluded from this study. Subjects will undergo MRI during the Screening period, which must demonstrate $\geq 8\%$ total liver fat content (LFC) by MRI-PDFF.

Subjects may be rescreened once with Medical Monitor approval. Note: certain laboratory parameters of interest (e.g., AST, TBL, creatinine clearance) may be retested at the investigators' discretion after discussing with the Medical Monitor.

On Day 1, eligible subjects will be randomized into one of the four treatment groups (0.3 mg aldafermin, 1 mg aldafermin, 3 mg aldafermin, or placebo) in a 1:1:1:1 ratio ([Table 3](#)). Randomization will be stratified by baseline stage of fibrosis (Stage 2 versus 3) on the qualification liver biopsy as determined by the Central Pathologist. Treatment assignment will be blinded to the investigational sites, study subjects, and sponsor (both Study Team and sponsor Medical Monitor or designee) throughout the study period and managed [REDACTED]. Study-drug self-administration instructions and training will be provided to the subjects and study-drug kits will be dispensed.

Table 3. Study Design

Study Treatment Group	Dose of aldafermin ^[1]	Mode of Administration	Volume of Injection ^[2]	Number of Subjects Planned
A	0.3 mg			38
B	1 mg			38
C	3 mg			38
D	Matched-Placebo			38
Total number of Subjects Planned:				152

^[1] In clinic dosing will occur on Day 1 and Study Week 2, 4, 8, 12, 18, and 24.

^[2] Presented in single-use prefilled syringes.

The first dose of aldafermin (Day 1) and doses at Weeks 2, 4, 8, 12, 18, and 24 study visits will be self-administered in the clinic, with all other daily doses through Week 24 self-administered at home. Self-administration should occur daily at a similar time at home. Subjects will return to the clinic on Weeks 2, 4, 8, 12, and 18 for on-treatment assessments and to receive aldafermin study-drug kits.

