12.2 Randomization

Eligible subjects will be randomized into one of the four treatment groups (0.3 mg aldafermin, 1 mg aldafermin, 3 mg aldafermin, or matched placebo) in a 1:1:1:1 ratio using a permuted block randomization schedule. Randomization will be stratified by baseline stage of fibrosis [REDACTED]

[REDACTED]

[REDACTED]

[REDACTED]

[REDACTED]

[REDACTED]

[REDACTED]

[REDACTED]

As such, the protocol will require a minimum of approximately 35% of subjects with F3 on biopsy. Depending on the overall enrollment rate and the proportion of subjects enrolled with F2 or F3, the sponsor may limit the enrollment of F2 subjects to be no greater than approximately 65% (99/152 subjects).

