12.5.2 Secondary Efficacy Analyses

Secondary efficacy analyses include the analyses of the primary efficacy endpoint (i.e., histologic response at Week 24) based on pair-wise comparisons between treatment groups and the analyses of the secondary efficacy endpoints.

All binary efficacy endpoints (i.e., responders) will be analyzed using a Cochran-Mantel-Haenszel (CMH) test stratified by baseline fibrosis stage.

All continuous efficacy endpoints will be analyzed using an analysis of covariance (ANCOVA) model with effects for treatment, baseline fibrosis stage and baseline outcome value as a covariate.

All secondary efficacy analyses will be performed using the ITT population. Full-Analysis, and PP populations will be used as sensitivity analyses.

No multiplicity adjustment will be made between the primary and secondary efficacy analyses to control the experiment-wise type I error rate, and thus all secondary efficacy analyses are exploratory in nature.

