#### 2.2 Data Conventions

The following data conventions will be used for all analyses described in this SAP.

- All subject-level data will be provided in data listings, unless stated otherwise.
- Study day will be calculated as:
  - o visit date first dose date, for screening visits;
  - o visit date first dose date + 1, for post-baseline/treatment visits.
- Baseline value will be defined as the last available, valid, non-missing assessment reported before the start of first study drug administration. The randomization date (and time, if available) will be used if the study drug start date is missing or not available for any reason.
- Change from baseline (change) is calculated as follow-up baseline. Percent (or relative) change from baseline (percent/relative change) is calculated as 100 × (change from baseline/baseline).
- Descriptive statistics including the number of non-missing observations (n), arithmetic mean (mean), standard deviation (SD), median, minimum (min), and maximum (max) will be presented for continuous endpoints. Frequency and percentage distribution will be presented for categorical endpoints. Kaplan-Meier estimates will be presented for time-to-event endpoints if applicable.
- Continuous endpoints will be analyzed using an analysis of variance (ANOVA) or analysis of covariance (ANCOVA) model. Ordinal categorical endpoints will be analyzed using a Wilcoxon rank-sum test. Nominal categorical endpoints will be analyzed using a Pearson's Chi-square test or Cochran-Mantel-Haenszel (CMH) test (A Fisher's exact test will be used if ≥ 25% of the cells have expected counts < 5). Time-to-event endpoints will be analyzed using a (stratified) log-rank test and Cox's proportional hazards model.

- Type III sums of squares will be used for all ANOVA and ANCOVA models.

- The level of statistical significance used for all statistical tests will be 0.05, unless stated otherwise. Statistical hypotheses for the primary efficacy analyses and the associated sensitivity analyses will be tested for statistical significance with two-sided alternatives, and one-sided alternatives will be used for all secondary and other efficacy analyses. All confidence intervals (CIs) will be two-sided, unless stated otherwise.
- Data from unscheduled visits will be presented in data listings, but will not be used for statistical analysis/summaries.

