## 5.1.6 Sensitivity Analyses

# 5.2 Secondary Efficacy Analyses

Secondary efficacy analyses will include treatment group comparisons of the fibrosis response (the primary efficacy endpoint) between each Aldafermin dose and placebo as well as the analyses of the following secondary efficacy endpoints:

- Subjects with resolution of NASH defined as an NAS score of 0 or 1 for inflammation and 0 for ballooning, with no worsening (compared to baseline) of fibrosis as determined by the NASH CRN criteria at Week 24
- Subjects with combined response of fibrosis improvement and NASH resolution, defined as subjects with an improvement in liver fibrosis by ≥ 1 stage with no worsening of steatohepatitis (no increase in NAS for ballooning, inflammation, or steatosis) and resolution of NASH as determined by the NASH CRN criteria at Week 24
- Subjects with improved, no change, and worsening of the following histological assessments at 24 weeks compared to baseline
  - o Fibrosis stage
  - NAS (total score and individual components)
- Subjects with the following changes in LFC by MRI-PDFF at Week 24:
  - o Normalization of LFC (defined as LFC < 5%)
  - $\circ \geq 5\%$  decrease from baseline in LFC
  - $\circ$   $\geq$  30% relative decrease from baseline in LFC
- Change and percent change from baseline to Week 24 in the following:
  - LFC by MRI-PDFF
  - o ALT, AST, total bilirubin, ALP, and gamma glutamyl transpeptidase (GGT)
  - Total cholesterol, high density lipoprotein cholesterol (HDL-C), LDL-C, and triglycerides
  - Lipoprotein particles
  - o Homeostasis model assessment-estimated insulin resistance (HOMA IR)
  - o N-terminal Type III collagen (Pro-C3)
  - o Total ELF Score and individual components (hyaluronic acid, PIIINP, TIMP-1)
  - o 7 alpha hydroxy 4 cholesten 3 one (C4) and serum bile acids (total and individual bile acids)
  - 0
- Subjects with normalization (i.e., values within the normal range) of ALT and AST at Week 24

For binary efficacy endpoints (i.e., responders), treatment group comparisons between each Aldafermin dose and placebo will be performed using the Cochran-Mantel-Haenszel (CMH) test stratified by baseline fibrosis stage. The treatment group difference of the response rates along with the corresponding 90% CI will be provided. The 90% CI will be constructed using the normal approximation method.

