For continuous efficacy endpoints, change and percent change from baseline will be analyzed using an analysis of covariance (ANCOVA) model with effects for treatment, baseline fibrosis stage and baseline outcome value as a covariate. Within the framework of the ANCOVA model, a point estimate of the treatment group difference between each Aldafermin dose and placebo will be provide along with the corresponding one-sided p-value and 90% CI.

All secondary efficacy analyses will be performed using the ITT analysis set. FAS and PP analysis sets will be used as sensitivity analyses. The missing data methods and sensitivity analyses described for the primary efficacy endpoint in Section 5.1 (for ITT and FAS analysis sets) will be used for the following histological endpoints:

- Fibrosis response
- NASH resolution
- Combined response of fibrosis improvement and NASH resolution

All statistical tests for the secondary efficacy analyses will be performed using a one-side test at the significance level of 5%, and no multiplicity adjustment will be made among these secondary efficacy analyses.

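### SAP 5.2 names no test for the improved / no change / worsening fibrosis and NAS endpoints, so they default to an unstratified Wilcoxon test; stratifying by stage is a near-free, low-priority improvement

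*SAP*

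**What the plan says.** Protocol section 7 (Study Design) states: "Randomization will be stratified by baseline stage of fibrosis (Stage 2 versus 3) on the qualification liver biopsy". Protocol 12.2 repeats that stage is the stratification factor.

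Among the secondary endpoints, SAP 5.2 lists "Subjects with improved, no change, and worsening of the following histological assessments at 24 weeks compared to baseline". The assessments are fibrosis stage and NAS, the latter as total score and as individual components.

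SAP 5.2 then gives methods for two kinds of endpoint:
- Binary endpoints get a CMH "test stratified by baseline fibrosis stage". Protocol 12.5.2 agrees.
- Continuous endpoints get an ANCOVA "model with effects for treatment, baseline fibrosis stage and baseline outcome value as a covariate".

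Neither SAP 5.2 nor Protocol 12.5.2 gives a method for a three-category ordered outcome. SAP 2.2, whose conventions are declared to cover every analysis in the SAP, has the only rule that fits: "Ordinal categorical endpoints will be analyzed using a Wilcoxon rank-sum test". The same item names a CMH test for nominal endpoints and marks the log-rank test as optionally stratified. It attaches no strata to the rank-sum test.

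On error rate, SAP 5.2 says "All statistical tests for the secondary efficacy analyses will be performed using a one-side test at the significance level of 5" per cent, without multiplicity adjustment. Protocol 12.5.2 calls all secondary efficacy analyses exploratory.

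**The concern.** When randomization is balanced within fibrosis stage, the treatment comparison carries almost no between-stage variation. The unstratified rank-sum test still counts that variation in its null variance. If stage predicts the outcome, the variance is too large, the test rejects less often than its nominal level, and some power is lost. The error runs in one direction only: it does not inflate false positives.

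On the default reading, these are the only secondary histology endpoints analysed without the randomization factor. NASH resolution and the combined response are binary and receive the stage-stratified CMH test. At stake are a little power on supportive endpoints, consistency within the SAP, and an analyst's choice that is better closed before unblinding.

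**Working it through.** **Inputs from the documents.** 38 randomized per arm, 15% drop-out, 32 evaluable per arm (SAP 1.3); one-sided 5% (SAP 5.2); F3 share of at least about 35% (Protocol 12.2; 35% and 50% are used here); fibrosis response 15% on placebo and 50% on 3 mg, with 30% and 42% among the Table 1 values for 1 mg (SAP 1.3).

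**Assumptions not in the documents.** Worsening 20% on placebo and 10 to 15% on active; a NAS-like case with improvement 40% against 65%; a common odds ratio (OR) of 1 to 10 linking F3 against F2 to a better category at both cut-points; drop-out that leaves the strata balanced.

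**Step 1: the plan's own figure.** The SAP states no power for these endpoints, only for the primary dose-response test. A maximum-contrast trend test with 32 per arm, two-sided 5%, and the six Table 1 shapes as candidates (the SAP's own candidate models are not visible) gives 93.2, 91.3, 93.4, 85.9, 88.7 and 90.6%, against the stated 92, 90, 93, 85, 87 and 90%. The null row gives 5.0%, against 5%. The sample-size inputs are therefore read correctly.

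**Step 2: why the size drops, by hand.** Take F3 share 35%, placebo 20 / 65 / 15% (worse / same / improved), stage OR 3.
- Stage rates solve 0.65·p2 + 0.35·p3 = overall rate, with the odds in the ratio 3. This gives F2 25.3 / 64.9 / 9.8% and F3 10.1 / 65.2 / 24.6%.
- Mid-rank scores: 0.20/2 = 0.10; 0.20 + 0.65/2 = 0.525; 0.85 + 0.15/2 = 0.925.
- Total variance: 0.20·0.10² + 0.65·0.525² + 0.15·0.925² − 0.5² = 0.0595.
- Mean scores are 0.4567 (F2) and 0.5804 (F3). Between-stage variance: 0.65·(0.0433)² + 0.35·(0.0804)² = 0.0035, or 5.8% of the total.
- The real variance is 94.2% of what the plain test assumes. The effective cut-off is 1.645/√0.942 = 1.695, and P(Z > 1.695) = 4.5%.

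**Step 3: simulation.** One dose against placebo, 32 per arm, 200,000 trials per setting, tie-corrected Wilcoxon against van Elteren stratified by F2/F3.

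Size of the plain test, across settings: 5.0% at OR 1, 4.8 to 4.9% at OR 2, 4.4% at OR 3, 3.6 to 4.0% at OR 5, 2.6 to 3.4% at OR 10. The stratified test stays at 4.9 to 5.1%. The hand value of 4.5% at OR 3 is in line with this.

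Power at F3 share 35%, plain / stratified (%):

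| Improved, placebo vs active | OR 1 | OR 3 | OR 5 |
|---|---|---|---|
| 15 vs 50 | 89.3 / 89.2 | 89.9 / 90.6 | 90.5 / 91.8 |
| 15 vs 42 | 72.4 / 72.2 | 72.8 / 74.2 | 73.7 / 76.6 |
| 15 vs 30 | 36.3 / 36.1 | 35.6 / 37.5 | 35.2 / 39.1 |
| 40 vs 65 (NAS-like) | 64.3 / 64.3 | 64.7 / 66.6 | 65.1 / 68.8 |

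Gain from stratifying, in points, over F3 shares of 35% and 50%:

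| Case | OR 1 | OR 2 | OR 3 | OR 5 | OR 10 |
|---|---|---|---|---|---|
| 15 vs 50 | −0.1 to −0.2 | 0.2–0.3 | 0.6–0.8 | 1.3–1.6 | 2.1–2.5 |
| 15 vs 30 | −0.1 to −0.2 | 0.7–0.8 | 1.9–2.2 | 3.9–4.5 | 7.4–8.3 |
| 40 vs 65 | −0.1 | 0.8–0.9 | 1.9–2.4 | 3.7–4.8 | 6.2–8.8 |

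With 38 per arm the gaps are similar or slightly smaller.

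**The case against.** **The SAP never assigns the Wilcoxon test to these endpoints by name.** The sentence in SAP 2.2 is a general convention. The categories could instead be split into improved yes/no and worsened yes/no under the stratified CMH test, or only tabulated. It is right that the assignment is by default, and a reader should not infer a deliberate decision to ignore stage. But SAP 2.2 covers all analyses in the SAP and contains the only rule for ordered categories, so the default follows from the text.

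**The loss depends on an unstated stage effect.** This stands in full. It is tempting to say that the plain test simply gives away power. The documents give no figure for how stage predicts change in fibrosis or NAS. F2 can worsen by more steps than F3, but the endpoint counts direction only, and both stages can move either way. For NAS and its components the documents offer no reason to expect a stage effect.

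**Large losses need extreme inputs.** Suppose placebo rates (worse / same / improved) of 35 / 50 / 15% in F2 and 3 / 50 / 47% in F3. The size of the plain test is then 3.4%, and power is 52.0% against 58.7% stratified if the treatment OR is 2.5. But the implied stage OR for worsening is (0.35/0.65)/(0.03/0.97), about 17. Nothing in the documents supports that.

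**A further inference is not supported.** The 12-week biopsy rule in Protocol 12.5.1 is written for the primary analysis, and SAP 5.2 extends the primary missing-data methods to three named endpoints only. A reader might conclude that improved fibrosis and fibrosis response rest on different subjects under conflicting biopsy rules. The text of SAP 5.1.2 (estimand) and 5.1.6 (sensitivity analyses) is not visible in the public copy, so the reach of the biopsy rule cannot be confirmed. Limiting imputation to named endpoints is an explicit choice. The two endpoints also differ by definition, because the response requires no worsening of steatohepatitis.

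**Conclusion.** The point holds as a low-priority improvement. By default, the three-category histology endpoints are tested without the factor that randomization is stratified by, while the binary and continuous secondary endpoints are adjusted for it.

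If stage is prognostic, the plain test is conservative. At a stage OR of 2 to 3 its one-sided size is about 4.4 to 4.9%, and it loses about 0.2 to 2.2 points of power in the fibrosis cases (up to 2.4 in the NAS-like case). At OR 5 the loss is about 1.3 to 4.5 points (up to 4.8 NAS-like). If stage is not prognostic there is no loss, and stratifying costs 0.1 to 0.2 points.

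These sizes rest on the assumed stage ORs, assumed worsening rates, proportional odds and balanced strata. The endpoints are exploratory and have no stated power, so no figure in the plan and no primary conclusion changes.

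**What to change.** Add to SAP 5.2, before unblinding: ordinal histology endpoints (improved, no change, worsening of fibrosis stage, NAS total and NAS components) will be compared between each aldafermin dose and placebo by the van Elteren test, that is, the CMH row-mean-score test with modified ridit scores, stratified by baseline fibrosis stage; the one-sided p-value is taken from the signed square root of the statistic.

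The cost is one sentence and one scoring option in CMH code that the trial needs anyway. No new data are required. The worst case is the 0.1 to 0.2 points of power lost if stage turns out not to matter.

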Low density lipoprotein cholesterol (LDL-C) will be evaluated at Weeks 2, 4, 8, 12 and 18 in all subjects for possible increases in lipid levels associated with Aldafermin administration. In statin naïve subjects, rosuvastatin will be started in subjects meeting specific LDL-C level criteria at Week 2. In statin experienced subjects, rosuvastatin (10mg OD in non-Asians and 5mg in Asians) will be started at Week 2. Rosuvastatin and matched placebo are over encapsulated to maintain the blind at the sites and with the sponsor study teams. Initiation and ongoing dose adjustments of rosuvastatin/matched placebo will be managed by an unblinded third-party medical monitor and through the ....... The sponsor and study sites will be blinded to LDL-C values and the specific rosuvastatin dosing decisions as outlined in Section 9.4.14 of the protocol. Subjects who have not achieved an adequate response or cannot tolerate rosuvastatin as defined in Section 9.4.14 of the protocol will be considered for the addition of ezetimibe as second-line lipid management therapy. Ezetimibe 10 mg tablets can be administered with or without food at the same time as rosuvastatin and Aldafermin or as monotherapy. Subjects whose LDL-C values are not adequately managed by their maximum tolerated rosuvastatin dose plus ezetimibe will be discontinued from study and an early withdrawal study visit will be completed. The follow-up/end-of-study (EOS) visit should be scheduled for 6 weeks after the early withdrawal study visit.

Rosuvastatin or matching placebo will be dispensed at each study visit through Week 18 (statin-naïve) or Week 24 (statin experienced). If the subject is taking over-encapsulated rosuvastatin or matched placebo, evaluate tolerability and continue therapy to Week 24 if statin naïve or Week 30 if statin experienced.

All subjects will return to the clinic at Week 25 for post-treatment LDL-C assessment. Subjects who have an LDL-C value of >100 mg/dL and > 15 mg/dL above their Day 1 value at Week 25 will be re-assessed at Week 30. Subjects who have an LDL-C value of > 100 mg/dL and >15 mg/dL above their Day 1 value at Week 30 will have an additional 4-week follow-up visit to confirm their LDL-C value is  $\leq$  100 mg/dL or  $\leq$  15 mg/dL above their Day 1 value.

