- Missing data for selected histological endpoints (e.g., primary and secondary) will be imputed using the methods as described in Section 5. Missing or incomplete dates for adverse events (AEs) and medications may be imputed as needed (e.g., to determine treatment emergence or distinguish between prior and concomitant medications) based on programming conventions. No imputations will be performed for missing or incomplete data of other types and, in this case, analyses will be performed based on the observed data only.

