## 5.3 Other Efficacy Analyses

The analyses of the secondary efficacy endpoints at Week 24 in Section 5.2 will also be performed for all other applicable visits.

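### Secondary tests are one-sided with no stated direction, which matters for LDL-C and total cholesterol; and the uncorrected normal-approximation 90% CI usually undercovers for the liver-fat responder endpoints

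*SAP*

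**What the plan says.** **Tests.** SAP 2.2 tests the primary two-sided, but "one-sided alternatives will be used for all secondary and other efficacy analyses". SAP 5.2 repeats the rule: "All statistical tests for the secondary efficacy analyses will be performed using a one-side test at the significance level of 5" per cent. SAP 5.3 extends it over time: "The analyses of the secondary efficacy endpoints at Week 24 in Section 5.2 will also be performed for all other applicable visits". The primary has a direction (an upward slope, SAP 5.1.5). No secondary endpoint has one in the visible text.

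**Lipids.** The SAP 5.2 list of change endpoints includes "Total cholesterol, high density lipoprotein cholesterol (HDL-C), LDL-C, and triglycerides". For these the ANCOVA gives an estimate that "will be provide along with the corresponding one-sided p-value and 90% CI". Protocol 5.4 says the drug raised total cholesterol and LDL-C in normal volunteers and in patients with type 2 diabetes. SAP 1.1 says that in statin-naïve subjects "rosuvastatin will be started in subjects meeting specific LDL-C level criteria at Week 2"; statin-experienced subjects switch to study rosuvastatin at the same visit.

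**Responder intervals.** SAP 5.2 pairs a stratified CMH test with a 90% interval for the difference: "The 90% CI will be constructed using the normal approximation method". No continuity correction is named or excluded. Only selected histology endpoints are imputed; SAP 2.2 adds that "No imputations will be performed for missing or incomplete data of other types". The three liver fat content (LFC) responses are therefore analysed as observed.

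**The concern.** A one-sided test needs a side. For LFC or ALT/AST responders the favourable side is obvious. For continuous endpoints it is not. For LDL-C and total cholesterol the natural efficacy alternative is a decrease, while the effect that the protocol anticipates is an increase. A test pointed at improvement returns a large p-value for a real rise.

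The interval is a separate matter. The uncorrected normal-approximation (Wald) interval is least reliable near 0% and 100%, and the LFC rates in Protocol 5.2.2 lie there. What is at stake is the lower confidence limit, which a reader takes as the smallest plausible benefit. If it is too high more often than the nominal 5%, the LFC result looks more certain than it is.

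**Working it through.** **Plan's own figure.** The SAP gives no power or coverage figure for secondary analyses. Its only figure is Table 1, for the primary: 92, 90, 93, 85, 87 and 90%. A max-contrast simulation with 32 per group, taking the six Table 1 shapes as candidate models (assumed; the real set is not visible), gives 93.3, 91.4, 93.7, 85.7, 88.4 and 89.8% two-sided, all within 2 points. One-sided it gives 91.8–96.6% and does not fit. So the primary is two-sided as stated.

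**A. Lipids at Week 2.** Inputs: 38 per group (SAP 1.1), or 32 after 15% drop-out (SAP 1.3). The documents give no SD or effect size, so rises of 0.3, 0.5 and 0.8 SD are assumed, as is a decrease for the alternative. With z = d/√(2/n), d = 0.5 and n = 38 give z = 0.5/0.2294 = 2.179. Then:
- chance of one-sided p < 0.05: Φ(−1.645 − 2.179) = 0.00007, about 0.0001
- median printed p: Φ(2.179) = 0.985
- two-sided 5% test detects the rise: Φ(2.179 − 1.960) = 59%
- planned 90% CI lies above 0: Φ(2.179 − 1.645) = 70%

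| Assumed rise, n | Chance p < 0.05 | Median p | Two-sided 5% | 90% CI above 0 |
|---|---|---|---|---|
| 0.3 SD, 38 | 0.002 | 0.90 | 26% | 37% |
| 0.5 SD, 38 | 0.0001 | 0.985 | 59% | 70% |
| 0.8 SD, 38 | <0.0001 | >0.999 | 94% | 97% |
| 0.5 SD, 32 | 0.0001 | 0.977 | 52% | 64% |

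**B. Coverage of the 90% interval.** Active rates are from Protocol 5.2.2, all at Week 12. Part 2 (single-blind) gives 57/90/100% for the ≥5% decrease and 17/24/69% for normalisation. Part 1 (double-blind) gives 74% for the ≥5% decrease and 85% for the ≥30% relative decrease, both at 3 mg. Placebo rates are from Part 1: 7% for both decreases (grid 4–10%) and none for normalisation (assumed 0–2%). The interval is d ± 1.645·√[p₁(1−p₁)/n + p₂(1−p₂)/n]. Both arms are enumerated exactly at n = 32 and averaged over a grid of true rates, because coverage oscillates with the rate. Upper misses for the decrease endpoints are the remainder, 100 − coverage − lower misses.

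| Endpoint, active rate | Average coverage | Lower limit too high | Upper limit too low | Coverage with continuity correction |
|---|---|---|---|---|
| Normalisation 17±5% | 87.3% | 3.2% | 9.5% | 94.2% |
| Normalisation 24±5% | 88.0% | 3.8% | 8.2% | 94.4% |
| Normalisation 69±5% | 88.2% | 7.7% | 4.1% | 94.4% |
| ≥5% decrease 57±5% | 88.6% | 6.7% | 4.7% | 94.0% |
| ≥5% decrease 74±5% | 88.2% | 8.2% | 3.6% | 93.9% |
| ≥5% decrease 90±3% | 87.1% | 10.6% | 2.3% | 93.6% |
| ≥5% decrease 95–100% | 84.0% | 14.3% | 1.7% | 91.8% |
| ≥30% relative 85±3% | 87.6% | 9.6% | 2.8% | 93.8% |

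Each tail is nominally 5%. In the 95–100% setting single grid points run from 72.1% to 91.9%. At n = 38 the ≥5% averages for the three Part 2 rates are about 89, 87 and 85%. Miettinen-Nurminen averages 89.9–91.1% in these settings. With two strata (21 + 11 per arm) at 95–100% v 4–10%, the normal approximation gives 84.4% and Miettinen-Nurminen 92.3%.

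**Example.** 32/32 v 2/32: difference 0.9375; SE √(0.0625 × 0.9375/32) = 0.0428; interval 0.9375 ± 0.0704, or 86.7% to 100.8%, past the possible maximum. Miettinen-Nurminen gives 82.7% to 97.9%.

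**Limits of the pattern.** At 2% v 2%, n = 38, coverage is 96.2%. At equal rates of 0–2% the interval lies wholly above 0 in at most 1.9% of trials. At 10–12% v an assumed 0–2%, n = 38 with complete data, the average is 87.2%, which is again undercoverage.

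**The case against.** A reader might infer that the lipid p-values cannot be interpreted, or that the plan hides a lipid rise. The documents do not support either. SAP 5.2 prints the estimate and a 90% CI beside each p-value. A positive LDL-C difference with p = 0.985 can only be a test for a decrease, and the reader can invert it. The safety laboratory tables (SAP 6.3) would show the rise as well. The planned 90% CI even excludes zero more often than the proposed two-sided test does.

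A reader might also extend the Week 2 figures to the listed Week 24 endpoint. That fails too: by then LDL-C is managed with rosuvastatin and, if needed, ezetimibe, so the documents do not establish a rise over placebo at Week 24.

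On the interval, the strongest objection is that a normal-approximation method may include a continuity correction. With one, every average above exceeds 90%, and the interval is conservative. The rates also combine two parts of an earlier study at Week 12, and the largest shortfall sits at the 100% boundary. At the double-blind 3 mg rate of 74% it is under 2 points. Nor does the interval always undercover or inflate false claims, as the equal-rate case shows. SAP 2.2 provides Fisher's exact test for sparse tables, but that does not repair the interval.

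All of this stands, and it limits the point. The direction is still unwritten, and the SAP still does not say which normal-approximation interval it means.

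**Conclusion.** Both parts hold, at a modest level.

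The lipid tests have no stated direction. Under an improvement alternative (assumed) they would almost never be significant for a rise, most clearly at Week 2, before study rosuvastatin takes effect. The size rests on assumed effects and on 32 to 38 subjects per arm. Only the p-value is affected.

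Read as the uncorrected Wald interval, the planned CI usually covers less than 90% for the LFC responders: about 87–89% in most settings, and 84% when the active rate is 95–100%. At high active rates the lower limit is too high in 7–14% of trials against a nominal 5%. At low active rates the misses fall mainly on the upper limit, so the possible benefit is understated.

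Protocol 12.5.2 calls these analyses exploratory. The primary conclusion is unaffected, and most LFC conclusions would not change, because the expected differences are so large.

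**What to change.** (a) In SAP 2.2, 5.2 and 5.3, test the lipid endpoints two-sided at 5% at every visit, and keep the estimate with a 95% CI to match. State the direction of the alternative for the other continuous one-sided tests, before unblinding. Cost: wording only. Downside: the 95% CI excludes zero less often than the planned 90% CI (59% v 70% at an assumed 0.5 SD, n = 38).

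(b) In SAP 5.2, for responder endpoints analysed as observed, replace the normal-approximation interval with a 90% Miettinen-Nurminen score interval stratified by baseline fibrosis stage. This covers the three LFC responses and, by the same rule although not calculated here, ALT/AST normalisation. Cost: a standard software option. Downside: wider intervals for sparse endpoints and less favourable lower limits at high response rates. The multiply imputed histology endpoints are outside this change, because the complete-data figures above do not carry over directly to pooled estimates.
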